### 9.4.1. Primary Endpoint

Phase 3: The primary analysis will utilize the ITT analysis set and a Cochran-Mantel-Haenszel test stratified by each of the actual stratification factors. Participants will be counted as failures once they go on a ventilator or die. Number and percentage of failures will be presented for each treatment arm. Cochran-Mantel-Haenszel p-values, estimated common odds ratios, estimated common risk differences, and corresponding approximate two-sided 95% CIs will be presented. The Breslow-Day test will be used to test the homogeneity of the odds ratios across strata. Although missing data are expected to be limited, any such cases will be imputed as failure. A supportive analysis using multiple imputation will be done in order to assess the sensitivity of the inference to the approach to missing data.

Phase 2: A similar methodology will be used; however, multiple imputation will not be done.

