### **6.4. Measures to Minimize Bias: Randomization and Blinding**

A randomized, double-blind, placebo-controlled study design was selected as the most robust design to minimize potential bias.

Participants who meet all applicable eligibility criteria will be centrally randomized to one of 2 study intervention groups (dociparstat or placebo) using an automated interactive response technology (IRT) system and a computer-generated randomization code provided by the sponsor or designee. Randomization of participants in Cohort 3 and in Phase 3 will be stratified based upon NIAID score (3 or 4) and age (<60 years vs  $\geq$ 60 years). Randomization of participants in Phase 3 will additionally be stratified by baseline BMI ( $<34 \text{ kg/m}^2$  or  $\geq 34 \text{ kg/m}^2$ ).

Once a randomization number has been assigned, it will not be re-assigned to any other participant in the study. The IRT system will also be used to track study intervention dispensing.

Investigators and participants will be blinded to each participant's assigned study intervention throughout the course of the study. In order to maintain this blind, an otherwise uninvolved third

party (an unblinded study pharmacist) will be responsible for the preparation and dispensation of blinded study interventions (i.e., dociparstat and placebo) and will ensure that there are no differences in appearance or time taken to dispense study intervention following randomization. In addition, the bolus syringe and the IV bags will be masked to obscure any visual differences in color between dociparstat and placebo.

In the event of a regulatory inspection or quality assurance audit, the auditor(s) will be allowed access to unblinded study intervention records at the site(s) to verify that randomization and dispensing have been done accurately. Additional roles and responsibilities that require unblinding of specified sponsor (and/or designated contract research organization) personnel not directly involved in the conduct of the study include supply chain, regulatory reporting of expedited safety reports, and DMC reviewers.

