### 9.2. Sample Size Determination

Approximately 600 potential participants are expected to be screened to achieve a total of approximately 75 participants randomized in Phase 2, and 450 participants randomized in Phase 3 of the study.

The sample size of 12 participants for Cohorts 1 and 2 was selected to assess for any major safety signals in a limited number of participants.

The sample size for Cohort 3 was selected to provide a reasonable level of precision to assess the treatment effect for the primary endpoint, specifically when the sample size is 51 randomized 2:1 dociparstat: placebo, a two-sided 95% confidence interval for the difference between a control failure rate of 20% and a dociparstat failure rate of 9% based on the large sample normal approximation will extend 21.3% from the observed difference in proportions.

For Phase 3, the sample size of 450 participants randomized 2:1 dociparstat: placebo was selected to detect the difference between a control failure rate of 20% and a dociparstat failure rate of 9% at a two-sided 0.05 alpha level with >80% power. This sample size also accounts for a futility analysis after 50% of the Phase 3 participants are enrolled using a Pocock beta spending function.

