## 9.4. Statistical Analyses

The SAP for Phase 2 will be finalized prior to the Cohort 3 analysis. The SAP for Phase 3 will be finalized prior to the first Phase 3 unblinded analysis. The SAPs will include a more technical and detailed description of the statistical analyses described in this section.

Phase 2: Data from Cohorts 1 and 2 will be analyzed and presented separately. Due to the evolving standard of care for COVID-19, the sponsor may decide to unblind and review study data following Cohort 1 and/or 2; therefore, one of two scenarios will inform the analysis approach for Cohort 3 as follows:

- In the event that Cohort 1 and 2 results remain blinded through Cohort 3 database lock, Cohort 3 data will be combined with either Cohort 1 or Cohort 2 data, depending on the selected dose.
- In the event that Cohort 1 and/or 2 results are unblinded prior to Cohort 3 database lock, Cohort 3 data will be analyzed and presented separately. In addition, Cohort 1, 2, and 3 data may be combined to support exploratory analysis.

Phase 3: Analysis sets will be presented separately (i.e., data from the Phase 2 portion of the study will not be used for the final confirmatory inference).

Descriptive analyses will be used to present Cohort 1 and Cohort 2 data.

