### **9.6. Data Monitoring Committee**

An independent unblinded DMC will review safety data from Cohort 1 to make a recommendation on dose escalation in Cohort 2, and will review safety data from both Cohorts 1 and 2 to make a recommendation on dosing in Cohort 3. The sponsor will consider the DMC recommendation when determining the actual doses for Cohorts 2 and 3. Due to the evolving standard of care for COVID-19, the sponsor may decide to unblind and review study data following Cohort 1 and/or 2. After completion of Phase 2, all data will be unblinded to the DMC and sponsor to determine whether the study should proceed with enrollment into Phase 3.

During Phase 3, the DMC will convene to review safety data after approximately 100, 225, and 350 participants complete the study. In addition, the DMC will review the pre-specified futility interim analysis.

The DMC will be provided with real-time, expedited safety reports to continue monitoring safety. The DMC chair may schedule ad hoc safety review meetings at any time during the study as deemed appropriate.

Details of the DMC membership and review procedures will be outlined in a separate charter.

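### Does the plan commit the Cohort 3 risk difference to a normal-approximation interval that under-covers at about three failures per arm?

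*Protocol*

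**What the plan says.** Protocol 9.2 sizes Cohort 3 at 51 participants, randomized 2:1, by the precision of a two-sided 95% interval for failure rates of 20% on control and 9% on dociparstat. The half-width, "based on the large sample normal approximation will extend 21.3% from the observed difference in proportions", is the only place where an interval type is named for this cohort.

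The analysis itself is in 9.4.1. For Phase 3 it plans a stratified Cochran-Mantel-Haenszel analysis in which "estimated common risk differences, and corresponding approximate two-sided 95% CIs will be presented". It then adds: "Phase 2: A similar methodology will be used; however, multiple imputation will not be done". No variance formula or interval method is given. The strata follow from 6.4: "Randomization of participants in Cohort 3 and in Phase 3 will be stratified based upon NIAID score (3 or 4) and age", so Cohort 3 has four cells; BMI is added only in Phase 3.

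Protocol 9.4 says where the rest belongs: "The SAP for Phase 2 will be finalized prior to the Cohort 3 analysis", and "The SAPs will include a more technical and detailed description of the statistical analyses described in this section". It also leaves open which data enter the analysis. If Cohorts 1 and 2 stay blinded, "Cohort 3 data will be combined with either Cohort 1 or Cohort 2 data, depending on the selected dose"; otherwise Cohort 3 stands alone. The SAP at hand covers only the analysis after the Cohort 1 or 2 lock (SAP section 1) and has no risk-difference interval for Cohort 3.

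**The concern.** Read together, 9.2 and 9.4.1 seem to point to a Wald-type interval for Cohort 3. The expected failures are few, about three in each arm, and are spread over four strata. Normal-type intervals for a difference in proportions are known to cover less than their nominal level at such counts, and the check below confirms it.

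The endpoint is a Phase 2 primary endpoint, and Cohort 3 was sized for the precision of this estimate. Under Protocol 9.6, once Phase 2 is complete, "all data will be unblinded to the DMC and sponsor to determine whether the study should proceed with enrollment into Phase 3". An interval labelled 95% that covers 92%, or less if event rates turn out lower, would overstate what is known when that decision is taken.

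**Working it through.** **Inputs.** Placebo 17 and dociparstat 34 (Protocol 4.1); failure rates 20% and 9%, two-sided 95% (9.2); four NIAID-by-age strata (6.4). Differences are placebo minus dociparstat, so positive values favour the drug. Stratum sizes, stratum risks and all rates other than 20%/9% are assumptions.

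**1. The plan's own figure.** Unpooled normal formula:

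1.96 × √(0.20×0.80/17 + 0.09×0.91/34) = 1.96 × √(0.009412 + 0.002409) = 0.2131

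This is the stated 21.3%. A pooled variance gives 19.4% and a continuity correction 25.7%. The formula uses arm totals only, so 9.2 is an unstratified calculation at assumed rates. It is not the stratified common difference of 9.4.1.

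**2. Expected failures.** 17 × 0.20 = 3.4 and 34 × 0.09 = 3.06.

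**3. Exact unstratified results**, enumerating both binomials (MN = Miettinen-Nurminen):

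| Placebo / drug | Wald coverage | MN coverage | Wald mean half-width | MN mean half-width |
|---|---|---|---|---|
| 20% / 9% | 92.5% | 94.8% | 20.4 | 21.6 |
| 30% / 15% | 92.3% | 95.4% | 24.1 | 24.0 |
| 20% / 20% | 93.0% | 95.2% | 22.5 | 23.4 |
| 15% / 7% | 90.8% | 95.4% | 18.0 | 20.2 |
| 10% / 5% | 82.6% | 94.6% | 14.8 | 18.6 |

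**4. Stratified results**, 60,000 simulated trials for each of three assumed strata patterns, Mantel-Haenszel weights. At 20%/9% the normal interval with Sato variance covers 91.7% to 92.0%, with mean half-width 19.8 to 20.5 points. Stratified MN covers 95.5% to 95.7%, with half-width 21.9 to 22.0. A stratum-wise unpooled variance covers only 88% to 89%. The size of the shortfall therefore depends on a variance formula that the documents do not name. At 10%/5%, Sato covers 82% to 83% and stratified MN about 97%, at a cost of 4.4 to 4.6 points of half-width.

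**5. Where the misses fall**, unstratified at 20%/9%:

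- Wald: upper limit too low in 5.94% of trials, lower limit too high in 1.52%. Coverage is 100 − 5.94 − 1.52 = 92.54%.
- MN: 1.65% and 3.59%. Coverage is 100 − 1.65 − 3.59 = 94.76%.

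Of Wald's 5.94 points, 5.85 arise when the observed effect is already adverse. MN has fewer misses in total but more than twice as many in the drug's favour. The same holds in less marked form under stratification: in 20,000-trial simulations the lower limit exceeds the truth in 2.9% to 3.0% of trials for MN, against 1.6% to 1.8% for Sato. With no true effect, at common rates of 10% to 20%, it exceeds zero in 2.9% to 3.3% against 1.1% to 2.3% (nominal 2.5%).

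**6. What a reader would see.** The most likely single result at the design rates is 3/17 against 3/34 failures (probability 5.6%). Wald gives −11.7 to +29.3 points and MN gives −9.7 to +33.7. The limits differ by 29.3 and 33.7 at the top (4.4 points) and by 2.0 points at the bottom. Both intervals include zero by a wide margin.

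**7. What the text commits to.** An MN interval is itself a large-sample approximation, so it satisfies the adjective used in 9.4.1 as well as a Wald-type interval does. A Phase 2 SAP naming stratified MN would contradict nothing in the protocol.

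**The case for a change.** The strongest case for the concern is that the author of the Phase 2 SAP inherits only the normal approximation in 9.2 and the loose wording of 9.4.1. The exact unstratified figures need no assumption about strata, and they show a real shortfall. It remains about 2 to 3 points at the higher rates tried and reaches about 12 points at 10%/5%. Lower event rates are conceivable while standard of care is changing, and naming an interval after seeing the data would be a data-dependent choice. A score interval costs only one line of text, and its mean half-width of about 22 points is barely wider than the planned 21.3.

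The coverage figures stand: a normal-type interval would be a weak choice for Cohort 3. What does not follow is that the plan makes that choice. A precision formula used for sizing does not bind the analysis, and the document that will settle the formula is due before the Cohort 3 analysis and is not among those available. Whether it names a score interval cannot be known from here. The 82% figure rests on rates that appear in neither document, and counting missing outcomes as failures (9.4.1) pushes observed rates up, not down. Nor is the alternative better in every respect: it is wider at the design rates and below, over-covers at low rates when stratified, and errs more often in the drug's favour, which matters when the question is whether to start Phase 3.

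**Conclusion.** The concern does not hold. The 21.3% is right, and nothing in either document ties the Cohort 3 analysis to the criticised interval. The missing formula is a detail that the protocol expressly assigns to a later SAP.

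If a normal-type interval were used, coverage at the design rates would be 92.5% unstratified, or about 92% stratified with Sato variance, instead of 95%. In the most likely result the limits would shift by about 2 and 4 points without changing the message. No numeric go/no-go rule depends on the interval, 9.4 keeps Phase 2 data out of the Phase 3 inference, and Cohorts 1 and 2 are descriptive only. Preferring Miettinen-Nurminen is a reasonable judgement between two kinds of error, not the correction of a mistake.

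The stratified figures rest on assumed strata sizes and risks; the unstratified ones at 20%/9% rest only on the protocol's own numbers. The conclusion about the text rests on the protocol and on a SAP limited to the Cohort 1 and 2 lock.

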#### **9.4.2. Secondary Endpoints**

Phase 3:

In the event the primary endpoint is met, the key secondary analysis of all-cause mortality at Day 28 will be tested sequentially at the 0.05 alpha level. This endpoint and other dichotomous secondary endpoints will use the same methods used for the primary endpoint.

For time-to-event secondary efficacy analyses, stratified log-rank p-values and hazard ratios from Cox proportional hazard models with 95% CIs will be presented. Median times to success/failure and corresponding 95% CIs will be presented for each group. For each endpoint, handling of participants who die during the study will be addressed in detail in the SAP.

Participants who are lost to follow-up will be censored at date/time of last follow-up.

The NIAID ordinal scale will be analyzed using the van Elteren test. The number and percentage of participants at each level will be summarized.

Continuous secondary analyses will be analyzed using analysis of variance (ANOVA), including stratification factors as independent factors. Treatment effects, corresponding 95% confidence intervals, and p-values will be presented. Rank ANOVA will be considered if normality assumptions governing use of parametric ANOVA are not supported. Analysis of covariance will be used if a baseline measure is available. Repeated measures analyses will be considered as appropriate.

The primary efficacy endpoint will be analyzed by various subgroups, including, but not limited to, each of the stratification factors, sex, and race (each race contributing  $\geq 10\%$  of participants plus other races grouped).

Phase 2: Similar methodologies will be used to analyze Phase 2 data.

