## 4. STUDY DESIGN

### 4.1. Overall Design

This is a randomized, double-blind, placebo-controlled, Phase 2/3 study to determine safety and therapeutic effect of dociparstat in adults with severe COVID-19 who are at high risk of respiratory failure.

Eligible participants hospitalized with laboratory-confirmed SARS-CoV-2, with a resting oxygen saturation (by pulse oximetry) of <94% on ambient air will be randomized to receive dociparstat or placebo for 7 days; both groups will also receive best supportive care (as determined by the investigator) as background therapy. The randomization ratio will be 1:1 in Cohort 1 and 2:1 (dociparstat: placebo) in all other cohorts. Randomization of participants in Phase 2/Cohort 3 and Phase 3 will be stratified by baseline score on the National Institute of Allergy and Infectious Diseases (NIAID) ordinal scale (3 or 4) and by age (<60 years or  $\geq$ 60 years). Randomization of participants in Phase 3 will additionally be stratified by baseline BMI ( $<34 \text{ kg/m}^2$  or  $\geq 34 \text{ kg/m}^2$ ).

Enrollment will be as follows:

- Phase 2
  - Cohort 1: 6 participants randomized to dociparstat, 6 randomized to placebo.
  - Cohort 2: 8 participants randomized to dociparstat, 4 randomized to placebo.
  - Cohort 3: 34 participants randomized to dociparstat, 17 randomized to placebo.
- Phase 3: 300 participants randomized to dociparstat, 150 randomized to placebo.

The primary efficacy endpoint is the proportion of participants who are alive and free of invasive mechanical ventilation through Day 28. Secondary endpoints include all-cause mortality, disease resolution, time to improvement, number of ventilator-free days, daily average of prednisone-equivalent corticosteroid dose, and change in potential biomarkers. Safety, including hematology, chemistry, and coagulation parameters and the incidence of AEs, severe AEs, and SAEs, will be assessed throughout the study.

After completion or discontinuation of study intervention, participants will be followed-up for outcomes through Day 28.

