### **9.5. Phase 3 Interim Futility Analysis**

A formal Phase 3 interim futility analysis will be conducted after 225 participants complete the study. The primary endpoint will be tested using a non-binding Pocock beta spending function boundary (futility bound 0.919). The study will not be stopped early for efficacy.

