Figure 5: Time to invasive mechanical ventilation, ECMO or all-cause mortality (KM-Plot) - ITT Set

Kaplan-Meier Plot:

y-axis:

range: 0% to 100% by 20%
label: Event-free Probability
reference-line: 50%

x-axis:

range: 0 to xxx (depending on data), by 7 days
label: Time to Event (Days)

Lines:

solid
different colors/line styles for the treatment-groups
starting at (100%/Baseline)
Censored values marked

Footnote:

N = Number of subjects in a specific group; (+) = censored values;

Kaplan-Meier estimates: Subjects with any invasive mechanical ventilation, ECMO or all-cause mortality will be counted as event.
All other subjects will be censored.

Time to first invasive mechanical ventilation, ECMO or all-cause mortality, whatever comes first (days): Days are calculated as
(start date/time - first study drug date/time)/24h). Time will be censored at last individual date/time reported. If time is not
available for events "00:01" will be imputed, for censored observations "23:59" will be imputed. Randomized untreated subjects will
be censored at time = 0.

(Notes for programmer: Subjects randomized not treated will be counted as censored observation (censor time = 0)

)

Table 19: Proportion of and time to all-cause mortality - ITT Set

	DSTAT 0.25 N=xxx	Cohort 1 PBO N=xxx	DSTAT 0.325 N=xxx	Cohort 2 PBO N=xxx
Number of subjects with all-cause mortality or early study discontinuation, n (%) (a)	xx (xx.x)	xx (xx.x)	xx (xx.x)	xx (xx.x)
Death	xx (xx.x)	xx (xx.x)	xx (xx.x)	xx (xx.x)
Early study discontinuation < Day 25	xx (xx.x)	xx (xx.x)	xx (xx.x)	xx (xx.x)
Kaplan-Meier estimates (b)				
Number of censored subjects, n (%) (b)	xx (xx.x)	xx (xx.x)	xx (xx.x)	xx (xx.x)
Time to all-cause mortality (days) (b)				
25% Quartile (95% CI)	x.x (x.xx,x.xx)	x.x (x.xx,x.xx)	x.x (x.xx,x.xx)	x.x (x.xx,x.xx)
Median (95% CI)	x.x (x.xx,x.xx)	x.x (x.xx,x.xx)	x.x (x.xx,x.xx)	x.x (x.xx,x.xx)
75% Quartile (95% CI)	x.x (x.xx,x.xx)	x.x (x.xx,x.xx)	x.x (x.xx,x.xx)	x.x (x.xx,x.xx)

N = Number of subjects in a specific group; n = Number of subjects with data available; Percentages are based on N;
 (a) Subjects with all-cause mortality or early study discontinuation before Day 25 will be counted as event.

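### By cross-reference, the alpha-tested Day 28 mortality analysis counts participants of unknown vital status as dead; mortality needs its own missing-data rule

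*Protocol*

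**What the plan says.** - Protocol 9.4.2 makes mortality the one secondary endpoint with a formal test behind the primary: "the key secondary analysis of all-cause mortality at Day 28 will be tested sequentially at the 0.05 alpha level".
- The same section gives its method by reference only: "This endpoint and other dichotomous secondary endpoints will use the same methods used for the primary endpoint".
- Protocol 9.4.1 describes the primary analysis as ITT with a stratified Cochran-Mantel-Haenszel test. It expects few missing outcomes and states that "any such cases will be imputed as failure". Multiple imputation is a supportive analysis in Phase 3.
- For time-to-event endpoints, which include time to all-cause mortality, 9.4.2 censors participants lost to follow-up.
- The supplied SAP covers only the analysis after the Cohort 1 or 2 lock. Footnote (a) of its Table 19 reads: "Subjects with all-cause mortality or early study discontinuation before Day 25 will be counted as event". Deaths and early discontinuations then appear on separate lines. The Kaplan-Meier part of the table treats only deaths as events and censors everyone else.
- Protocol 9.4 says that a separate Phase 3 SAP will be finalized before the first unblinded Phase 3 analysis.

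**The concern.** For a composite of ventilation or death, counting a missing outcome as failure is a familiar convention. For mortality the only failure is death, so the same rule records deaths that nobody observed. Someone discharged alive who later withdraws consent or cannot be traced would enter the tested comparison as a death.

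The resulting quantity is not 28-day mortality. It is the proportion dead or unknown. If equal shares are unknown in both arms, the ratio of the two proportions moves toward 1 and power falls. If the shares differ, the difference in missingness enters the estimate as a difference in mortality, in whichever direction it happens to run. At stake is the only secondary claim that the plan protects with alpha.

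**Working it through.** **Inputs from the documents.** Phase 3 allocation is stated in Protocol 4.1: "Phase 3: 300 participants randomized to dociparstat, 150 randomized to placebo". Protocol 9.2 gives the primary failure rates as 20% (control) and 9% (dociparstat), tested "at a two-sided 0.05 alpha level with >80% power". Protocol 9.5 gives a futility bound of 0.919 after 225 participants.

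**Inputs assumed.** The documents give neither the expected mortality nor the share with unknown status. I take 12% versus 5% mortality as the main case and 0–5% missing, independent of outcome.

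**Plan's own figure first.** With d the risk difference, s0 the pooled standard error and s1 the unpooled one, power = Φ[(d − 1.96·s0)/s1].
- 20% versus 9%, 150:300: (0.11 − 1.96 × 0.03326)/0.03660 = 1.22, power 0.89. With unpooled variance throughout, 0.85.
- With the 0.919 bound at half the information and unpooled variance, 0.804. The stated >80% reproduces.

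**Effect of the rule.** If true mortality is p and a share m is unknown, the analysed rate is q = p + m(1 − p).

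| Missing in both arms | Analysed rates, placebo vs dociparstat | Risk ratio | Power |
|---|---|---|---|
| 0% | 12.0% vs 5.0% | 0.42 | 74% |
| 1% | 12.9% vs 6.0% | 0.46 | 69% |
| 2% | 13.8% vs 6.9% | 0.50 | 65% |
| 3% | 14.6% vs 7.9% | 0.54 | 61% |
| 5% | 16.4% vs 9.8% | 0.60 | 53% |

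The 3% row as an example: q = 0.12 + 0.03 × 0.88 = 0.1464 and 0.05 + 0.03 × 0.95 = 0.0785, so (0.0679 − 1.96 × 0.03015)/0.03278 = 0.27, power 0.61.

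Dropping the missing participants instead would leave power at 73% (3% missing) and 72% (5%), so the loss comes from the imputation rule and not from the smaller sample. The risk difference itself shrinks only by the factor 1 − m: at 5% missing, 7.0 × 0.95 = 6.65 points. Other assumed pairs behave alike at 5% missing: 10% vs 5%, power 52% to 33%; 15% vs 7%, 75% to 58%; 10% vs 4%, 69% to 46%.

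**No true mortality effect.** Equal missingness leaves the two-sided rejection rate at 5.0%. With 8% mortality in both arms and unequal missingness, ignoring the gate:
- Placebo 5% missing, dociparstat 2%: analysed 12.6% vs 9.84%; rejection 15.4%, of which 15.1 points are toward benefit.
- Placebo 2%, dociparstat 5%: rejection 12.8%, of which 12.7 points are toward harm.
- 3% versus 2%: 6.4% if placebo has more missing, 5.7% if dociparstat has.

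At 5% versus 2% missing the totals are 15.8–19.8% when mortality is 5% in both arms and 11.6–13.6% when it is 10%.

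**With the gate.** Mortality is tested only after a positive primary result. I simulated 8% mortality in both arms, with the same participants missing for both endpoints. If the true primary failure rate is also equal, at 20%, false mortality-benefit claims occur in about 5% of trials when placebo has 5% missing and dociparstat 2%, and in about 0.1% when the shares are reversed. If the primary effect is real (20% versus 9%) and placebo has more missing, the rate returns to about 15%.

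**The case against.** **The text may not mean this.** Section 9.4.2 nowhere says that unknown status is death; a reader could take the cross-reference to cover only the test and the effect measures. That is possible. But 9.4.1 presents the missing-data rule as part of the primary method, no section sets another rule for mortality, and the Cohort 1/2 SAP follows the same convention. A reader might go further and infer that the Phase 3 rule is already fixed. The documents do not support that, because the detailed Phase 3 SAP is still to come.

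**Table 19 is not the tested analysis.** This stands. It describes cohorts of 12 participants each, without inference. A reader might also infer that the table reports two contradictory mortality results. It does not: the top row is labelled as death or early discontinuation, deaths have their own line, and both conventions are footnoted. The table shows the sponsor's convention and no more.

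**Safeguards exist.** Protocol 7.3 expects follow-up to Day 28 after treatment stops, and 7.4 asks sites to verify vital status. If the primary methods carry over, so does the supportive multiple imputation. Time to death is analysed with censoring. These limit the missingness and would expose a discrepancy, but none of them is the alpha-tested result.

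**The rule avoids a missing-at-random assumption.** True. That is a reason to keep it as a sensitivity analysis. It does not make the rule conservative, since its direction depends on which arm loses more people.

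**Conclusion.** The concern holds as a gap that should be closed in the Phase 3 wording. Followed as written, 9.4.1 and 9.4.2 together count unknown vital status as death in the tested mortality comparison.

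The predictable cost is lost power: about 5 points at 1% missing and 21 points at 5%, on the assumed 12% versus 5% mortality. Bias needs unequal missingness, and the documents give no particular reason to expect it in a blinded 28-day trial. A reader might take the 13–15% rejection rate as the trial's false-positive rate for mortality. It is not. It ignores the gate and adds both directions together. A false benefit claim at about that rate requires a real effect on ventilation, no effect on mortality, and clearly more missing data on placebo. All sizes here rest on assumed mortality and missingness, and on missingness independent of outcome. If missing data prove as limited as 9.4.1 expects, the effect is modest.

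**What to change.** In Protocol 9.4.2 and the Phase 3 SAP, give Day 28 mortality its own rule:

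1. Only documented deaths count as observed events.
2. Unknown Day 28 vital status is treated as missing and handled in the main analysis by the multiple imputation already planned, or by a stratified Kaplan-Meier estimate of Day 28 risk.
3. Missing = death is reported as a sensitivity analysis.

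The cost is wording, settled before the first unblinded Phase 3 analysis. The small downside is that the main mortality result then relies on a missing-at-random assumption, which the retained sensitivity analysis tests. Making the Death line the headline row of SAP Table 19 is an optional change of presentation.

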### 3. OBJECTIVES AND ENDPOINTS

Objectives	Endpoints
Primary – Phase 2	

 
To select maximally tolerated dose for use in Phase 3, and to assess the effect of dociparstat on disease progression in participants with severe COVID-19
 
	
 
Incidence of AEs, severe AEs, and SAEs
 
Proportion of participants who are alive and free of invasive mechanical ventilation through Day 28
 

Primary – Phase 3	

 
To assess the effect of dociparstat on disease progression in participants with severe COVID-19
 
	
 
Proportion of participants who are alive and free of invasive mechanical ventilation through Day 28
 

Key Secondary	

 
To assess the effect of dociparstat on mortality
 
	
 
All-cause mortality through Day 28
 

Secondary	

 
To determine additional evidence of a therapeutic effect of dociparstat in participants with severe COVID-19
 
	
 
Time to invasive mechanical ventilation or all-cause mortality
 
Time to all-cause mortality
 
Proportion of participants who are alive, discharged from the hospital, and not using home oxygen at fixed time points (Days 8, 14, and 28)
 
Clinical status assessed by the NIAID ordinal scale at fixed time points (Days 8, 14, and 28)
 
Time to clinical improvement, defined as time to at least a 2-grade improvement from baseline on the NIAID ordinal scale
 
Number of ventilator-free days from baseline through Day 28
 
Time to hospital discharge
 
Time to resolution of fever, defined as temperature <math>\leq 99.0^{\circ}\text{F}</math> (<math>\leq 37.2^{\circ}\text{C}</math>) and no antipyretic use within the preceding 48 hours (participants with baseline fever only)
 
Change from baseline in C-reactive protein level
 
Change from baseline in serum ferritin level
 
Change from baseline in lactate dehydrogenase level
 
Change from baseline in d-dimer level
 
Daily average of prednisone-equivalent corticosteroid dose through Day 28
 

Objectives	Endpoints

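### In Phase 3, a pooled-variance ANOVA interval for ventilator-free days is too narrow under 2:1 allocation if dociparstat works: about 92% coverage at the design rates (minor)

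*Protocol*

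**What the plan says.** Protocol section 3 lists "Number of ventilator-free days from baseline through Day 28" among the secondary endpoints that are not key. Section 9.4.2 sets the method for endpoints of this type: "Continuous secondary analyses will be analyzed using analysis of variance (ANOVA), including stratification factors as independent factors". It promises a treatment effect, a 95% interval and a p-value. The one fallback is conditional: "Rank ANOVA will be considered if normality assumptions governing use of parametric ANOVA are not supported". Neither sentence mentions unequal variances, a Welch correction or a robust standard error.

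Section 4.1 gives the arm sizes: "Phase 3: 300 participants randomized to dociparstat, 150 randomized to placebo". Section 9.2 gives the design rates: "control failure rate of 20% and a dociparstat failure rate of 9% at a two-sided 0.05 alpha level with >80% power".

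The supplied SAP (section 3) scores a participant who dies as 0. Everyone else gets study duration, capped at 28 days, minus days on invasive ventilation or ECMO. That SAP covers only the analysis after Cohorts 1 and 2 and summarises this endpoint descriptively (Table 23), so it does not settle the Phase 3 method. Protocol section 9.4 defers technical detail to a Phase 3 SAP, to be finalised before the first unblinded Phase 3 analysis.

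**The concern.** Participants who stay alive and unventilated to Day 28 sit at or near 28. Nearly all the variance therefore comes from those who fail. At the design rates about 20% of placebo and 9% of dociparstat participants fail, so the placebo variance is about twice the dociparstat variance. Since Amendment 3 changed the allocation from 1:1 to 2:1 (Appendix 10, Table 10), placebo is also the smaller arm.

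A pooled variance weights each arm by its size, so the low-variance arm dominates. The true standard error of the difference depends mostly on the small, high-variance arm. The pooled standard error is then too small. Sample size does not cure this, because the ratio of pooled to true standard error depends on the allocation and the variance ratio and does not approach 1 as the trial grows. At stake is a reported benefit in days that looks somewhat more precise than it is.

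**Working it through.** **Inputs.** Failure rates 20% and 9%, two-sided alpha 0.05 (protocol 9.2); arms of 150 and 300 (4.1); scoring from the SAP, assumed to carry over to Phase 3. The distribution of ventilator-free days among failures is not in the documents, so it is assumed and varied.

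**The plan's own figures.** Power for 150 against 300 at 20% against 9% is 89.0% with pooled variance and 85.2% unpooled. If the futility bound of 0.919 is read as a Z value at half the information and treated as binding, power is 80.4%. The claim of more than 80% reproduces. The Cohort 3 half-width, 1.96 × √(0.20×0.80/17 + 0.09×0.91/34) = 21.3%, reproduces exactly.

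**Base case: failures score 0, all others 28.**
- Placebo variance: 28² × 0.20 × 0.80 = 125.4 (SD 11.2 days).
- Dociparstat variance: 28² × 0.09 × 0.91 = 64.2 (SD 8.0 days). Ratio 1.95.
- True SE: √(125.4/150 + 64.2/300) = 1.025 days.
- Pooled SE: √[(149×125.4 + 299×64.2)/448 × (1/150 + 1/300)] = 0.920 days.
- Ratio: 0.920/1.025 = 0.897, so the SE is about 10% too small.
- Coverage: 2Φ(1.965 × 0.897) − 1 = 92.2%.
- Half-width: 1.81 days, where 2.01 is needed. The expected difference is 28 × 0.11 = 3.08 days.

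**Other assumptions for failures** (half at 0 and half uniform 0–27; all uniform 0–27; mean 10, SD 9; mean 20, SD 5): analytic coverage is 92.0% to 92.1%.

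**Simulation**, 20,000 trials per row, with treatment plus three binary stratification factors in the model:

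| Setting | Pooled ANOVA | HC3 |
|---|---|---|
| 300/150, 20% vs 9%, three failure distributions, factors prognostic or not | 91.6–92.4% | 94.4–95.0% |
| 225/225, 20% vs 9% | 95.1% | 95.2% |
| 300/150, 20% vs 20% | 95.0% | 94.9% |

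**How far it extends** (analytic, pooled variance, 300/150):

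| Change from the base case | Coverage |
|---|---|
| 20% vs 12% | 93.3% |
| 20% vs 15% | 94.2% |
| 30% vs 20% | 94.0% |
| 20% vs 9%, 2% early discontinuation in both arms | 92.4–92.7% |
| Same, 5% | 92.7–93.1% |
| Same, 10% | 93.0–93.7% |
| Placebo 9%, dociparstat 20% (harm) | 97.2% |

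Discontinuers are assumed uniform on 0–27. Letting completers' scores vary with the Day 28 visit window (assumed mean 26.9, SD 1.2) leaves the case without discontinuation at 92.2% to 92.3%.

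**The case against.** The strongest reply is that the plan already doubts parametric ANOVA for data like these. With 80% to 91% of participants at one value, normality plainly fails and the rank ANOVA trigger is met. The variance estimator is also ordinary SAP detail, and the Phase 3 SAP is not among the documents. Part of this stands: the protocol never states equal variances, so the point rests on the default meaning of ANOVA, and the later SAP can settle it. But the fallback is only to be considered, responds to non-normality rather than unequal variance, and yields no interval in days. It does not repair the promised interval.

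Several stronger readings are tempting and are not supported:

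- **That coverage is 92% whenever the drug works.** That figure belongs to the design rates with little discontinuation. Smaller effects or discontinuation common to both arms bring it to about 93% to 94%. If the drug did harm, the interval would be too wide.
- **That false-positive findings become more likely.** When the two distributions are equal, so are the variances, and coverage is 95.0%.
- **That the trial's conclusion is at risk.** The primary endpoint uses a Cochran-Mantel-Haenszel test, and only mortality is tested in sequence after it. No futility or success decision uses this interval.
- **That the p-value should move to the van Elteren test.** That test addresses a different quantity from a mean difference in days and could disagree with the interval. It is not needed.

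**Conclusion.** The concern holds as a minor point about one interval. With pooled-variance ANOVA, 300/150 allocation and failure rates of 20% and 9%, the standard error for ventilator-free days is about 10% too small and coverage is about 92%, or non-coverage near 8% instead of 5%. In the base case the half-width is short by 2.01 − 1.81 = 0.20 days, about 5 hours, against an expected benefit of 3.08 days. Either interval centred on that benefit excludes zero.

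The result rests on four assumptions: the default reading of ANOVA, the SAP's scoring carrying into Phase 3, the design failure rates, and little early discontinuation. It barely depends on how ventilator-free days are distributed among failures. It would disappear under equal allocation or with no treatment difference.

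**What to change.** Add one sentence to section 9.4.2 or the Phase 3 SAP: for ventilator-free days, keep the linear model with treatment and the stratification factors, and compute both the 95% interval and its matching p-value with a heteroscedasticity-robust standard error (HC3, or a Welch-type equivalent). Using one standard error for both keeps them consistent.

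In simulation, HC3 restores coverage to 94.4% to 95.0% at 300/150. The cost is an interval about 12% wider at the design rates (1/0.897 = 1.11 in the base case; 1/0.892 = 1.12 with failures at mean 20, SD 5), which is roughly the width needed for 95% coverage. The allocation, sample size and primary analysis do not change. The sentence should be in place before the first unblinded Phase 3 analysis.
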